### **2.2.3 Withdrawal and Lost-to-Follow-up**

Patients may be withdrawn from the study for a number of reasons. The following is a summary of the possible reasons for withdrawal.

Subjects may voluntarily withdraw from the study. The reason for withdrawal must be documented on the Termination CRF (Attachment E).

After the implant procedure, some subjects may not return for follow-up visits. A minimum of three (3) attempts to contact such patients must be made. All attempts are to be documented on the Termination CRF.

Subsequent to enrollment, if new information demonstrates that a patient does not meet the inclusion/exclusion requirements, the patient must be withdrawn from the study. The reasons for withdrawal must be documented on the Termination CRF. If such information is not discovered until after the implant procedure, the patient will still be followed for safety reasons but will not be included in the final analysis.

In some cases, an implant procedure will be initiated (i.e., an attempt to pass or deploy the device) but is aborted prior to device deployment. Such patients maintain their enrollment status (since this is an intent-to-treat study) but need not

be followed. On the other hand, if a patient is initially screened and enrolled, but no procedure is ever initiated, the patient is cancelled and his/her enrollment position is made available to another patient.

Patients who are enrolled in the study group and are converted to surgery due to peri- or post-implantation complications will be followed for a minimum of 12 months after enrollment. Conversion to surgery is documented on the Procedure CRF.

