#### **2.2.6.2. Conversion to Surgery**

In some subjects there may be difficulty inserting the Medtronic/Talent System during the procedure. If it is not possible to complete implantation of the device, or if peri- or post-operative complications arise that place the subject at risk, the Clinical Investigator/Sponsor may elect to convert the patient to open surgery. Alternatively, the Clinical Investigator/Sponsor may elect not to repair the TAA, and to manage the patient with observation only. In such cases, the reason for conversion must be recorded on the Procedure CRF.

Also, as noted previously, subjects who convert to surgery or who are managed by observation will be followed in an identical manner as the other subjects. A Post-Operative Assessment CRF will be completed at 1, 6, and 12 months after the attempted implantation.

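### Section 2.2.3 excuses follow-up of patients whose procedure is aborted before deployment, while 2.2.6.2 and 2.1.3 require it, so unreported post-discharge events and deaths in these patients can go uncollected

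*Protocol*

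**What the plan says.** Section 2.2.3 describes cases in which "an implant procedure will be initiated (i.e., an attempt to pass or deploy the device) but is aborted prior to device deployment". Its rule for them is: "Such patients maintain their enrollment status (since this is an intent-to-treat study) but need not" be followed. The same section treats two neighbouring groups differently:

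- Before any attempt: "if a patient is initially screened and enrolled, but no procedure is ever initiated, the patient is cancelled", and the place is given to someone else.
- After a complication: patients "converted to surgery due to peri- or post-implantation complications will be followed for a minimum of 12 months after enrollment".

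Section 2.2.6.2 applies, among other triggers, "If it is not possible to complete implantation of the device". The investigator may then convert to open surgery, or "may elect not to repair the TAA, and to manage the patient with observation only". On follow-up it states that "subjects who convert to surgery or who are managed by observation will be followed in an identical manner as the other subjects", and adds: "A Post-Operative Assessment CRF will be completed at 1, 6, and 12 months after the attempted implantation".

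Section 2.1.3 says that all 50 subjects are followed for life under the Lifeline Registry protocol. Section 2.1.2 makes safety the primary objective. Section 2.2.4 lists among the outcomes the proportion of patients with adverse events, both during the procedure and afterwards, and overall mortality.

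**The concern.** Keeping a patient in an intent-to-treat population only helps if the patient's outcome is known. Section 2.2.3 keeps the aborted patient in the study and in the same sentence drops the obligation to find out what happened next. Section 2.2.6.2 imposes that obligation on what is largely the same group.

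Section 2.2.3 is also hard to reconcile with itself. A patient found ineligible after the implant procedure is left out of the final analysis but still followed for safety. A patient whose procedure is aborted is retained as intent-to-treat but need not be followed.

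At stake are post-discharge adverse events and deaths that no one volunteers. Any loss would fall only on patients in whom delivery failed, which is part of what a safety study of a delivery-dependent device should describe. An analysis plan can set out how to handle missing outcomes, but it cannot restore outcomes that were never sought.

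**Working it through.** **Step 1. Do the rules reach the same patients?** Section 2.2.3 defines its group by an attempt to pass or deploy that stops before deployment. Section 2.2.6.2 opens with difficulty inserting the system, covers failure to complete implantation, and counts its visits from the attempt rather than from an implant. It therefore includes patients who never received a device.

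| Patient | 2.2.3 | 2.2.6.2 | Compatible? |
|---|---|---|---|
| No procedure initiated | Cancelled, place reused | Not addressed | Yes |
| Aborted before deployment, observed | Need not be followed | Followed like other subjects | No |
| Aborted before deployment, converted without a complication | Need not be followed | Followed like other subjects | No |
| Converted because of a complication | At least 12 months from enrollment | Followed like other subjects | Yes: a minimum allows more |

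In rows 2 and 3 the waiver also conflicts with lifelong follow-up of all 50 subjects in 2.1.3.

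**Step 2. What other text still captures outcomes in rows 2 and 3?**

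- 2.2.5.5: a pre-discharge examination for all study group patients. This covers the hospital stay.
- 2.2.6: adverse experiences that a subject reports or the investigator notes are recorded. This covers spontaneous reports.
- 2.2.5.7: a Termination form for every subject. The final-assessment contact, however, is worded for patients who received an implant.
- 2.2.7: each patient is monitored at set intervals after treatment. This may or may not extend to a patient whose treatment was aborted.
- 2.2.5.6: visits are timed from the implant procedure, with no statement on attempted implants.
- 2.3.3: lifelong follow-up is promised to patients who receive the stent-graft.

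What remains exposed is post-discharge events and deaths that nobody reports, if the waiver is the rule applied.

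**Step 3. Size.** The protocol gives no abort rate and no figure to reproduce. Inputs: N = 50 (2.1.3), taken as the denominator; k = unfollowed patients discharged alive, an assumption.

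Mortality proportion left undetermined = k / 50:

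- k = 1: 1/50 = 2 points
- k = 3: 3/50 = 6 points
- k = 5: 5/50 = 10 points

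Example with k = 3 and an assumed 4 deaths among the 47 followed: between 4/50 = 8% and 7/50 = 14%.

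For the proportion with any adverse event, only patients still event-free at discharge count, because the others are already events. With k = 3 and 0, 1, 2 or 3 of them event-free, the undetermined part is 0, 2, 4 or 6 points.

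The direction of any bias is not fixed. With k = 5 and 5 deaths observed, dividing by all 50 gives 10.0%, and dividing by the 45 followed gives 11.1%.

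**The case against.** The best case for the protocol is that the gap is narrow and partly covered. In-hospital and reported events are captured. Section 2.2.7 promises monitoring of each patient. Sections 2.2.1 and 2.2.2 make availability for follow-up a condition of entry. Section 2.2.5.1 has patients given a separate registry consent. The Lifeline Registry protocol and the Appendix F chart of procedures are not shown and may schedule these patients. All of this stands, and it limits the claim to unreported post-discharge outcomes. It does not remove the contradiction, because 2.2.3 still excuses what 2.2.6.2 requires.

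The denominator is also open to challenge. Section 2.2.4 describes an evaluation of patients receiving the device, and 2.2.3 removes patients found ineligible after implantation from the final analysis. That is why the 2-point figure is conditional on all 50 being counted.

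A reader might infer three stronger things that the document does not support:

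- *That the 12-month rule for conversions cuts follow-up short.* It is stated as a minimum, so a patient followed as 2.1.3 and 2.2.6.2 require also satisfies it. Its different starting point, enrollment rather than the attempt, is a matter of wording.
- *That different sites will follow different rules.* The visible text mentions several investigators but does not state that there are several sites. The problem is two rules in one document.
- *That the number of aborted patients can be predicted from the series in 1.1.* The 103 of 108 successes concern a homemade device and combine thrombosis with technical success. The 25 of 26 concern a different device. Neither gives an abort rate for this one.

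**Conclusion.** The contradiction is real and should be corrected. For patients aborted before deployment and then observed, or converted without a complication, 2.2.3 cannot be reconciled with 2.2.6.2 and 2.1.3 as written. The conflict is clearest for the observed group.

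If 2.2.6.2 is followed, nothing is lost. If the waiver in 2.2.3 is followed, unreported post-discharge adverse events and deaths may go uncollected in patients in whom delivery failed. The number of such patients is unknown and may be very small. With 50 as the denominator, each one discharged alive and not followed leaves 2 percentage points of mortality undetermined. No direction of bias is claimed, nor that all outcomes of these patients are lost. The conclusion rests on the visible text; the registry protocol and the procedures chart could narrow the practical gap but would not make the two sections agree.

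**What to change.** Reconcile 2.1.3, 2.2.3 and 2.2.6.2. Delete the follow-up waiver in 2.2.3 and replace it with a cross-reference to 2.2.6.2, so that adverse events and vital status are collected for every patient with an initiated procedure, on the 1-, 6- and 12-month form schedule timed from the attempted implantation. State how lifelong follow-up under 2.1.3 applies to patients without an implant.

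As wording points, align the starting point of the conversion minimum in 2.2.3 with that schedule, and extend the final-assessment contact in 2.2.5.7 beyond implant recipients. Whether patients without an implant need imaging is a clinical question for the sponsor and is not part of this change.

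The cost is a few sentences in 2.2.3 and 2.2.5.7, a clarification in 2.1.3, and assessments that 2.2.6.2 already requires.

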# **1. Report of Prior Investigations**

## **1.1 Introduction**

A vascular aneurysm is a permanent, localized dilatation of a blood vessel at least 1 1/2 to 2 times the normal vessel diameter. The aorta is the most frequent site for aneurysms, with approximately 10% of aortic aneurysms located above the renal arteries in the thoracic segment. (Coselli and LeMaire, 1995.) Thoracic aortic aneurysms (TAAs) are less common than abdominal aortic aneurysms, however, detection of TAAs is increasing, perhaps due to an aging population, increased diagnostic capability or an increase in prevalence. (Mitchell, Miller and Dake, 1997.) Ascending and transverse arch aneurysms each comprise 25% of TAAs; the remaining 50% occur in the descending thoracic aorta. The most common cause of TAA is medial degenerative disease of the aortic wall, responsible for most ascending aortic aneurysms and most fusiform aneurysms involving the descending aorta. Arteriosclerosis, commonly found superimposed on aneurysmal disease of other etiologies, frequently results in saccular aneurysms. Additional causes of TAA are dissection, aortitis, trauma, and infection. (Coselli and LeMaire, 1995.) In cases of aortic dissection, which typically involves the descending thoracic aorta, the origin of the dissection is in the proximal descending aorta in about 25% of the cases. Traumatic TAA is typically caused by blunt chest trauma that produces partial aortic disruption. (Coselli, Buket and Crawford, 1996.)

Untreated thoracic aneurysms can be life-threatening. As many as 78% of untreated patients with TAA die within 5 years after diagnosis, most often from

rupture of the aneurysm. (Pressler and McNamara, 1980.) Conventional surgical treatment, either tube graft replacement or patch aortoplasty, is a high-risk surgical procedure. Repair of the descending thoracic aorta is performed with a thoracotomy and cross-clamping of the aorta, with or without a shunt by-pass to maintain distal perfusion. Cardiopulmonary bypass is used to control rising blood pressure. (Najafi, 1994.) Mortality associated with surgical repair of the thoracic aorta ranges from 12% to more than 50%, depending on the urgency of the procedure, coexisting debilitating diseases or conditions, and the patient's general health. (Moreno-Cabral, Miller, Mitchell, et al, 1984.)

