### **2.1.3 Duration of the Investigation**

Accrual of study subjects will occur over approximately 3 years with all 50 subjects to be followed according to the Lifeline Registry of Endovascular Repair protocol for the life of the patient (Please see Attach C for the protocol).

---

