#### **2.2.4 Study Design**

This study is a prospective evaluation of patients receiving the investigational device to determine the proportion in whom successful implantation is achieved, as indicated by aneurysm exclusion and graft patency at implant, time of discharge, and 1-, 6-, and 12-months following implantation, and to determine the proportion of patients who experience adverse events during and after the implantation procedure, including comorbidities and overall mortality rates. The percentage of patients in whom technical and clinical success is achieved, and the percentage who experience serious adverse effects will be determined. Additional endpoints that will be evaluated are length of stay in intensive care following the procedure, total length of hospital stay and recovery time.

Patient data and follow-up information and images will be stored with the Lifeline Registry for Aneurysm Repair with periodic reports to the FDA up to the 5-year follow-up supplemented with reports from the Registry database.

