The Stent-Graft for thoracic implantation is a straight tubular design. Depending on the patient's aortic and aneurysm anatomy, the stent-graft may be supplied as a single section or a modular multi-section system. Additional sections, referred to as extensions, may be added as needed (e.g., if a leak resulting from incomplete exclusion of the aneurysm (endoleak) is discovered either during the implantation procedure or post procedure). Each section is introduced separately into the vasculature and mated in vivo to sections already in situ. All sections are composed of a metal stent coupled to a fabric vascular graft. The metal stent frame is made of small diameter nitinol monofilament wire with a titanium oxide coating formed into a-series of ring-like zig-zag springs connected by connecting bars. The stent is sewn with suture to the lumen of a proprietary low-permeability polyester material. This material is thinner than the Meadox and Bard graft materials used in the first-generation system, but is it is chemically-equivalent in its composition.

The Talent stent-graft system will be custom built for each patient (i.e., patient-specific).

Anatomical measurements from each patient are used to manufacture a stent-

graft. The stent-graft can vary in diameter, length, end design, and axial cross-section (cylindrical tube versus tapered tube), as required for each patient's anatomy.

Depending on physician preference and specific anatomical requirements, the proximal and distal ends of the Talent stent-graft are available with or without coverage with the polyester fabric. In the uncovered version (referred to as the bare spring design) there is an additional 1.5 cm length (nominal) spring that is uncovered and is joined to the most proximal or distal spring of the stent-graft. The bare spring design is intended to allow placement of the most proximal or distal portion of the device across involved arteries (e.g., the left subclavian artery) that originate from the aorta. The covered version is referred to as the open web design and may be used when the device is not intended for placement adjacent to a patent vessel.

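### The protocol calls the study intent-to-treat, but its own rules define a set of eligible patients with an attempted implant, and deaths between enrollment and procedure enter no stated rate.

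*Protocol*

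**What the plan says.** Protocol 2.2.3 (Withdrawal and Lost-to-Follow-up) treats three groups differently.

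- **Procedure started but aborted before deployment.** These patients stay in: "Such patients maintain their enrollment status (since this is an intent-to-treat study".
- **Enrolled, procedure never started.** The rule applies "if a patient is initially screened and enrolled, but no procedure is ever initiated". In that case "the patient is cancelled and his/her enrollment position is made available to another patient".
- **Found ineligible after the implant.** These patients are still followed for safety but are left out of the final analysis.

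Other sections bear on the point.

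- 2.1.3 (Duration of the Investigation) gives the planned size: "Accrual of study subjects will occur over approximately 3 years with all 50 subjects to be followed".
- 2.2.4 (Study Design) opens: "This study is a prospective evaluation of patients receiving the investigational device". It counts adverse events, and mortality with them, from the procedure onward.
- 2.4.1 (Stent-Graft) states: "The Talent stent-graft system will be custom built for each patient (i.e., patient-specific". The patient's own anatomical measurements supply the specification.
- 1.1 (Introduction) gives the natural history: "As many as 78% of untreated patients with TAA die within 5 years after diagnosis", with rupture the usual cause.
- 2.2.5.7 (Final Assessment) requires a Termination form for each subject, whatever the reason for ending participation.

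**The concern.** Intent-to-treat means that everyone enrolled stays in the analysis, whatever happens next. Section 2.2.3 relies on that principle to keep aborted attempts. It then sets the principle aside twice: for enrolled patients who never reach the procedure, and for implanted patients later judged ineligible. A reader who relies on the label will take the reported rates to describe all enrolled patients, and they will not.

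The patients removed before the procedure are unlikely to be a random subset. Death, rupture and deterioration are among the reasons a planned procedure does not start, and each such patient is replaced by one who did reach it. As a description of all enrolled patients, mortality would then tend to come out too low. This matters most for the overall mortality that 2.2.4 promises, and for the hypothesis in 2.2.6.4 that serious events will be fewer than expected with surgery.

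The post-implant exclusion is the plainer departure, because it removes patients who have already been exposed to the device from a study whose primary objective is device safety.

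**Working it through.** The plan gives no figure to reproduce. The 50 subjects are stated without an error rate, power or reference rate. The check has two parts.

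**1. Which set do the rules produce?**

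| Patient group | Rule in 2.2.3 | In the final analysis? |
|---|---|---|
| Enrolled, no procedure started | Cancelled, place refilled | No |
| Procedure started, aborted | Keeps enrollment status | Yes |
| Implanted, eligible | Ordinary follow-up | Yes |
| Implanted, later found ineligible | Followed for safety only | No |

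The two Yes rows make up eligible patients with an attempted implant. That is neither intent-to-treat nor all attempted implants. This result needs no numbers.

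**2. How many waiting deaths could be left out?**

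The order of events implies a wait. Patients consent (2.2.5.1), are then evaluated and measured for sizing (2.2.5.2 and 2.2.5.3), and receive a graft built from those measurements (2.4.1). Neither the length of the wait nor the exact moment of enrollment is stated, so what follows is illustration.

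Inputs:
- Five-year mortality untreated: 78% (1.1, worded there as an upper figure).
- Hazard: assumed constant.
- Wait *m*: assumed 0.5 to 3 months.
- Number enrolled: 50.

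Formulas:
- Monthly hazard *h* = −ln(1 − 0.78)/60 = 1.5141/60 = 0.02524.
- Risk of death while waiting *p* = 1 − exp(−*h m*).
- Expected deaths = 50*p*.
- Chance of at least one death = 1 − (1 − *p*)^50.

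| Assumed wait (months) | *p* | Expected deaths per 50 enrolled | Chance of at least one |
|---|---|---|---|
| 0.5 | 1.25% | 0.6 | 47% |
| 1 | 2.49% | 1.2 | 72% |
| 2 | 4.92% | 2.5 | 92% |
| 3 | 7.29% | 3.6 | 98% |

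At these low risks the expected count is nearly proportional to the hazard, so a lower true hazard shrinks it by about the same factor.

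To see the effect on a reported rate, assume 5 deaths among the 50 analysed. The rule as written reports 5/50 = 10.0% (exact 95% interval 3.3% to 21.8%). With *k* waiting deaths restored, the rate is (5 + *k*)/(50 + *k*):
- *k* = 1: 6/51 = 11.8%
- *k* = 2: 7/52 = 13.5%
- *k* = 3: 8/53 = 15.1% (exact 95% interval 6.8% to 27.6%)

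**The case against.** The strongest reply is that the protocol never sets out to estimate the outcome of a treatment strategy in all enrolled patients. Its primary objective (2.1.2) is device safety in use, and 2.2.4 evaluates patients who receive the device. Someone who never reaches the procedure has no exposure. The study has no randomisation to protect, and the term appears once, in parentheses, directly before the replacement rule. Nothing shows that the surgical mortality cited in 1.1 counts deaths before the operation, so adding waiting deaths on the stent-graft side could make that comparison less like-for-like. This stands as far as the choice of set goes: an attempted-implant set is defensible and replacement may stay. It does not rescue the label, and it does not cover implanted patients dropped for ineligibility, who were exposed.

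A second reply is that a disposition table or a supporting analysis usually belongs in the SAP, which is not shown. That is fair for the detail. But the protocol itself fixes both the label and the removal rules, and these conflict as written.

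A reader might infer that cancelled patients leave no trace. The documents do not support that. Section 2.2.5.7 asks for a Termination form for every subject, so the event may well be recorded, provided a cancelled patient still counts as a subject. The form and the registry protocol are attachments not shown here. What is missing is any stated rate that such an event would enter.

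A reader might also take the 11.8% to 15.1% range as the bias in this trial. It is not. The wait and the five deaths are assumed, and the 78% is an upper figure for untreated aneurysm, while dissections, ulcers, transections and pseudoaneurysms are also enrolled. Even 15.1% lies well inside the 95% interval for 5/50.

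**Conclusion.** The point holds as one of labelling and accounting. Section 2.2.3 claims intent-to-treat, while its own rules yield eligible patients with an attempted implant. Deaths or ruptures between enrollment and procedure fall outside every rate the protocol names, and implanted patients later found ineligible fall outside the final analysis. These conclusions rest on the text alone.

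The size of any effect on mortality is unknown. The figure of about 0.6 to 3.6 omitted deaths per 50 enrolled depends on an assumed wait of 0.5 to 3 months, a constant hazard, and the upper 78% figure applied to every lesion type. It shows that the omission could matter in a study of 50, not that it will. The documents do not show that the device-safety result in treated patients is biased by replacement, nor that the events go unrecorded. The correction is still worth making, because it is cheap and changes what the reported rates can be taken to mean.

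**What to change.** 1. In 2.2.3, replace the intent-to-treat description with an accurate one: the analysed set consists of patients in whom the procedure was attempted.
2. In the same place, state how patients found ineligible after the implant are handled. Preferably keep them in the safety results, since they were exposed to the device.
3. Keep replacement if wanted, but account for every enrolled patient in the report, cancelled ones included, with the reason for cancellation and vital status. State that the existing Termination form is completed for cancelled patients and is the source.
4. Give all-cause mortality from enrollment in all enrolled patients as a supporting figure beside the rates in the attempted set.

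The cost is one extra table. The supporting mortality figure may also be slightly less favourable than the figure for attempted implants.
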